3.7.4 Vital Signs

Descriptive statistics for vital signs and changes from baseline values at each scheduled time point will be presented by treatment group. Additionally, number and percentage of subjects with values considered PCS occurring at any time post-baseline will be summarized by treatment group. Criteria for PCS are presented in Table 5.

Table 5: Criteria Potentially Clinically Significant (PCS) Blood Pressure or Pulse Rate

Parameter	PCS Criterion
Systolic blood pressure, supine	Low: ≤ 90 mm Hg and decrease ≥ 20 mm Hg
	High: ≥ 180 mm Hg and increase ≥ 20 mm Hg
Diastolic blood pressure, supine	Low: ≤ 50 mm Hg and decrease ≥ 15 mm Hg
	High: ≥ 105 mm Hg and increase ≥ 15 mm Hg
Pulse, supine	Low: ≤ 50 bpm and decrease ≥ 15 bpm
	High: ≥ 120 bpm and increase ≥ 15 bpm

All vital signs will be presented in the subject data listing.

Orthostatic hypotension (20/10) is defined as a fall in systolic blood pressure of at least 20 mmHg and a fall in the diastolic blood pressure of at least 10 mmHg upon standing from supine. Orthostatic hypotension (30) is defined as a fall in systolic blood pressure of at least 30 mmHg upon standing from supine.

Orthostatic tachycardia is defined as a heart rate increase of 30 beats per minute (bpm) or more upon standing from supine, or over 120 bpm upon standing.

The number and percentage of subjects with orthostatic hypotension or orthostatic tachycardia occurring at any post-baseline timepoint will also be summarized by treatment group.

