This is Alkermes' first study of the co-administration of olanzapine and samidorphan in a population of adults with schizophrenia. In addition, this study includes higher doses of samidorphan than the 5-mg dose that was used in a prior study (ALK33-301). Samidorphan has been associated with somnolence, and olanzapine has been associated with orthostatic hypotension. In ALK33-301, there was no apparent additive effect of the co-administration on either of these adverse effects. However, because the current study involves higher doses of samidorphan than studied previously, it was desired to take a conservative approach by monitoring subjects in an inpatient setting for 2 nights following randomization (Visit 3) and transition (Visit 13).

During clinic visits, assessments of psychotic symptoms using measures such as the PANSS and CGI-S will occur. Body weight will be measured using consistent methods at every visit. Alcohol and drug use will be monitored throughout the study. Concentrations of samidorphan, RDC-9986 (primary metabolite of samidorphan), and olanzapine will be determined in plasma samples collected at Visits 2-23.

8.1.1. Part A (Screening, Olanzapine Lead-In, and Double-Blind Placebo-Controlled Treatment Period)

Screening assessments will occur in the 30-day period before subjects report to the clinic for verification of eligibility and initiation of olanzapine treatment (Study Day 1). On Study Day 1 (Visit 2), all eligible subjects will be initiated on olanzapine. Olanzapine dose will be selected and titrated by the PI based upon individual subject needs and consistent with current clinical practice. Subjects will return one week later (ie, Study Day 8, Visit 3) for a 2-night inpatient stay and the start of the 12-week double-blind placebo-controlled treatment period. At this visit, subjects will be randomized in a 1:1:1:1 ratio to receive samidorphan (5 mg, 10 mg, or 20 mg) or placebo. Olanzapine dosing will continue uninterrupted. Thus, the Part A treatment groups will be as follows:

- Olanzapine + Samidorphan (5 mg)
- Olanzapine + Samidorphan (10 mg)
- Olanzapine + Samidorphan (20 mg)
- Olanzapine + Placebo

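### The categorical summary of orthostatic hypotension in SAP 3.7.4 leaves out systolic falls of 20-29 mmHg with a diastolic fall below 10, and every diastolic fall of 10 or more with a systolic fall below 20; rows for each component would close the gap.

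*SAP*

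**What the plan says.** SAP 3.7.4 gives two postural blood pressure definitions. The (20/10) category requires "a fall in systolic blood pressure of at least 20 mmHg and a fall in the diastolic blood pressure of at least 10 mmHg" on standing from supine. The second reads: "Orthostatic hypotension (30) is defined as a fall in systolic blood pressure of at least 30 mmHg upon standing from supine". Both feed one by-arm count: "The number and percentage of subjects with orthostatic hypotension or orthostatic tachycardia occurring at any post-baseline timepoint will also be summarized by treatment group".

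The other blood pressure criteria in that section, in SAP Table 5, apply to supine values: "Low: ≤ 90 mm Hg and decrease ≥ 20 mm Hg" for systolic and "Low: ≤ 50 mm Hg and decrease ≥ 15 mm Hg" for diastolic. They do not classify a fall on standing. The section also plans descriptive statistics by scheduled time point and states: "All vital signs will be presented in the subject data listing".

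Protocol 8.1 explains the two 2-night stays. It says: "Samidorphan has been associated with somnolence, and olanzapine has been associated with orthostatic hypotension". It adds that the earlier combination study showed no apparent additive effect on either, but that samidorphan doses here go above the 5 mg used there, so a cautious approach was wanted. Protocol 8.3.6 and Tables 1 and 2 schedule supine and standing readings before dosing and about 1 hour after it at Visits 3-6 and 13-16.

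**The concern.** The trial goes to some trouble to collect supine and standing pressures around the first samidorphan doses, and the SAP then counts only part of what those readings can show. A systolic fall of 30 counts whatever the diastolic does, but 29/9 does not. A diastolic fall never counts by itself, however large.

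Somnolence, the other effect named in Protocol 8.1, has its own adverse event category in SAP 3.7.2.2.1 (under sedation). That section has no category for hypotension, dizziness or syncope, so the count in SAP 3.7.4 carries the categorical reporting of postural blood pressure alone. If samidorphan shifted mainly one component of the postural response, that count could show little difference between arms of about 70 subjects.

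**Working it through.** The documents state no rate for orthostatic hypotension, so there is no planned figure to reproduce.

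**1. Logic.** Let S and D be the systolic and diastolic falls on standing. The SAP counts (S≥20 and D≥10) or S≥30. Readings that cross a 20/10 limit but are not counted are exactly:
- 20≤S<30 with D<10 (for example 25/5, 29/9);
- D≥10 with S<20 (for example 15/12, 19/25).

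A check on integer falls (S from -10 to 60, D from -10 to 40) gave these two regions and no others. Readings of 20/10, 30/5 and 35/0 are counted.

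**2. Share of readings.** Every input here is an assumption. Mid case: bivariate normal, means 3/0, SD 10/8, correlation 0.5.
- P(S≥20) = 1-Φ(17/10) = 0.045
- P(D≥10) = 1-Φ(10/8) = 0.106
- P(both) = 0.018
- P(either) = 0.045+0.106-0.018, about 0.132 before rounding of the terms
- SAP definitions together: about 0.020, so 0.020/0.132 = 15% of readings crossing a limit are flagged

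Over systolic means 0-6 (SD 10-12), diastolic means -2 to +2 (SD 8-9) and correlations 0.3-0.7, that share is 7%-35%.

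**3. Subjects.** SAP 3.7.4 counts a subject flagged at any post-baseline time. Part A has 8 such readings: Visit 3 post-dose (1), Visits 4-6 pre- and post-dose (6), Visit 13 pre-dose (1). With independent readings in the mid case and no drug effect:
- SAP definitions: 1-(1-0.0196)^8 = 15%
- Either limit: 1-(1-0.132)^8 = 68%
- S≥20: 1-(1-0.0446)^8 = 31%

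With within-subject correlation up to 0.7, the first two become 8%-15% and 36%-68%.

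**4. Visibility of an arm difference.** No test is planned; power only measures how visible a difference would be. For n=70 per arm (SAP 2), one dose against placebo:

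power ≈ Φ{(|p1-p0| - 1.96√[2p̄(1-p̄)/n]) / √[(p0(1-p0)+p1(1-p1))/n]}

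Example, S≥20 row, +4 mmHg systolic, independent readings: P(S≥20) becomes 1-Φ(1.3) = 0.097, so p1 = 1-(0.903)^8 = 0.56 against p0 = 0.31, and power is about 0.86.

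Mid case, within-subject correlation 0 / 0.3 / 0.5 / 0.7 (simulated, so the second decimal can move by 0.01-0.02):

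| Shift (S/D) | SAP rules together | Either limit | Row for the shifted component |
|---|---|---|---|
| +4/0 | 0.42 / 0.31 / 0.25 / 0.20 | 0.24 / 0.19 / 0.17 / 0.14 | S≥20: 0.86 / 0.67 / 0.55 / 0.45 |
| 0/+3 | 0.11 / 0.09 / 0.08 / 0.07 | 0.66 / 0.48 / 0.41 / 0.35 | D≥10: 0.84 / 0.65 / 0.57 / 0.48 |
| +4/+2 | 0.69 / 0.52 / 0.42 / 0.35 | 0.68 / 0.54 / 0.47 / 0.40 | S≥20: 0.86 / 0.67 / 0.55 / 0.45 |

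Over a wider set of assumed inputs, a systolic-only shift gives 20%-50% for the SAP rules together and 67%-87% for the S≥20 row. A diastolic-only shift gives 8%-9% and 46%-71% for the D≥10 row. An either-limit row flags about 22%-77% of subjects with no drug effect.

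**The case against.** The strongest reply is that nothing in the documents is contradicted. Neither document gives another definition or cites a reference one. The wording may well be deliberate: the tachycardia definition that follows uses *or*, Table 5 uses compound *and* rules, and the (30) category picks up large isolated systolic falls. The rule is the same in every arm. All of this stands, so a reader who infers a drafting slip goes further than the text allows.

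A reader might also infer that the omitted falls go unreported. They do not. Listings hold every value, descriptive statistics are given by arm and time point, investigator-reported events enter the treatment-emergent adverse event tables (SAP 3.7.2.1), and the DSMB reviews accumulated safety data. The gap is in the categorical summary only. Nor are the stays about this effect alone, since somnolence is named beside it.

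Finally, a low flag rate is not the same as low sensitivity to an arm difference, and replacing *and* with *or* looks like the obvious remedy but is a trade-off. In the mid case it lowers power for a systolic-only shift (0.24 against 0.42 with independent readings) and roughly ties when both components move. This objection defeats the one-word change. It does not reach separate component rows.

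**Conclusion.** The point holds as a gap in tabulation. Which readings are left out follows from the SAP wording alone and needs no assumption. The consequence is that a drug effect concentrated in one component would be poorly visible in the only pre-defined categorical summary of a named safety interest. How poorly depends on assumed means, SDs, correlations and shifts, none of which the documents supply, so the percentages are illustrations. When both components shift, no single row is best across the inputs tried, which is a reason to keep the existing rows as well.

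A reader might conclude that the plan would hide an excess at 20 mg. The documents do not support that: they contain no effect estimate, and the other safety outputs remain. This is a cheap improvement that leaves the primary analysis and the conduct of the study untouched.

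**What to change.** In SAP 3.7.4 and the matching mock table, keep the (20/10) *and* row and the (30) row. Add three by-arm rows, using the same any-post-baseline rule:
- systolic fall ≥20 mmHg, whatever the diastolic change;
- diastolic fall ≥10 mmHg, whatever the systolic change;
- either limit met.

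Add a sentence giving the reason for the joint (20/10) rule. Do not simply change *and* to *or*. Make the change before the database lock and unblinding by which Protocol 14.2 requires the SAP to be final; rows added later should be labelled post hoc.

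The readings are already scheduled, so no new data are needed. The cost is a few table rows, counts in the new rows at least as high as the (20/10) count in every arm, and more descriptive comparisons to interpret with care.

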3.7.5 Electrocardiograms

Descriptive statistics for ECG parameters (heart rate, RR interval, PR interval, QRS interval, QT interval, QTcB [QT interval corrected using Bazett's method], QTcF [QT interval corrected using Fridericia's method]) and changes from baseline values at each scheduled time point will be presented by treatment group. Any other ECG parameters that are collected will be presented in the listings only.

In addition, the number and percentages of subjects with any post-baseline results meeting supra-threshold QTc criteria, as defined in Table 6, based on ICH (International Conference on Harmonization) Guidance E14[3] will be presented by treatment for QTcB and QTcF. A listing will present all values for a subject and parameter for cases where at least one value for that parameter was potentially significant.

Table 6: Abnormal results for Electrocardiogram

Parameter	Abnormal ECG Results Criteria
QTcB, QTcF	
 • >500 milliseconds 
 ○ >60 millisecond change from baseline ○ >30 - <=60 millisecond change from baseline • >480 and ≤500 milliseconds 
 ○ >60 millisecond change from baseline ○ >30 - <=60 millisecond change from baseline • >450 and ≤ 480 milliseconds 
 ○ >60 millisecond change from baseline ○ >30 - <=60 millisecond change from baseline • >60 millisecond change from baseline • >30 - <=60 millisecond change from baseline

3.7.6 Prior and Concomitant Medications

Prior medications are defined as medications taken prior to the first dose of the randomized study medication. Concomitant medications are defined as medications taken during the treatment period. Concomitant medications for Part A placebo-controlled period are defined as medications taken between the first dose of the randomized medication to the end of Part A treatment period (inclusive). Concomitant medications for Part B ALKS 3831 treatment period are defined as medications taken between the first dose of the samidorphan to the end of Part B treatment period (inclusive).

All medications as documented by the investigator will be coded using the World Health Organization Anatomical Therapeutic Chemical (WHO-ATC) drug dictionary, version March 2012.

Prior and concomitant medications will be summarized by the Preferred Term and by treatment group. Medication taken only during the follow-up period will be presented in the subject data listing only. For the summary tables, if a subject has taken a prior or concomitant medication more than once, the subject will be counted only once for the medication. Partial date imputation for medications is described in Section 3.11.5. All reported medications will be presented in the subject data listing.

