
- Olanzapine + Samidorphan (5 mg)
- Olanzapine + Samidorphan (10 mg)
- Olanzapine + Samidorphan (20 mg)
- Olanzapine + Placebo

All study drug will be taken once daily by mouth. Olanzapine and samidorphan/placebo tablets should be taken together (ie, at the same time). Randomization will be stratified by the amount of weight change during the olanzapine lead-in period (ie, from Day 1 to Day 8), with subjects grouped into the following 3 strata:

- Weight change ≤ 0 kg
- Weight increase >0 to <1 kg
- Weight increase ≥ 1 kg

Subjects will be discharged from the inpatient unit on Study Day 10 (Visit 5) and will return on Study Day 15 (Visit 6).

Subjects are not required to be taking any antipsychotic medication at the time of screening or Visit 2. However, those who are will be tapered off of their prior antipsychotic medication within two weeks after initiation (ie, by Study Day 15, Visit 6). This cross-taper from prior antipsychotic treatment to olanzapine will be conducted under the care and discretion of the PI and consistent with current clinical practice.

After Study Day 15 subjects will return to the clinic weekly through the first month of double-blind treatment (ie, Study Day 36) and then every 2 weeks thereafter for the remainder of Part A. Any subject who prematurely discontinues during Part A will be asked to return to the clinic for an early termination (ET) visit and will be asked to return for follow-up visits 2 and 4 weeks later.

Part A Visit Schedule

	Screening	Olanzapine Lead-In	Double-Blind Placebo-Controlled Treatment Period										Transition*
Visit	1	2	3	4	5	6	7	8	9	10	11	12	13
Day	-30 to -1	1	8	9	10	15	22	29	36	50	64	78	92
Week			1			2	3	4	5	7	9	11	13

* Transition (Visit 13) is the end of Part A and the beginning of Part B (Part B begins with dosing at Visit 13). Shaded cells represent inpatient stays.

Assessments prior to study drug administration at Visit 13 (the transition visit) will serve as end of Part A assessments; dosing and post-dose assessments will be considered Part B assessments.

Part B (Active ALKS 3831 Treatment and Safety Follow-up Periods)

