9.3. Randomization and Blinding

Part A of this study will be conducted in a double-blind fashion. On Day 8 (Visit 3), subjects will be randomized to receive one of the following regimens in a 1:1:1:1 ratio:

- Olanzapine + Samidorphan (5 mg)
- Olanzapine + Samidorphan (10 mg)
- Olanzapine + Samidorphan (20 mg)
- Olanzapine + Placebo

Randomization will be performed centrally through an IWRS system and will be stratified by the amount of weight change during the olanzapine lead-in period (ie, from Day 1 to Day 8), with subjects grouped into the following 3 strata:

- Weight change ≤ 0 kg
- Weight increase >0 to <1 kg
- Weight increase ≥ 1 kg

Alkermes staff, clinical staff, and subjects will remain blinded to treatment assignment until Part A of the study is complete. All ^{PPD} staff will remain blinded except when their study function requires unblinding (eg, drug supply management, IWRS operation, DSMB operation, etc). These unblinded staff will follow procedures designed to ensure that study integrity is maintained.

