1.2 SUMMARY OF THE STUDY DESIGN

This is a Phase 2, randomized, placebo-controlled multicenter study that is divided into 2 parts: Part A and Part B.

Part A will begin with screening followed by a 1-week olanzapine lead-in period where subjects will receive olanzapine daily and a 12-week double-blind, placebo-controlled treatment period where subjects will receive samidorphan or placebo (in addition to the olanzapine prescribed on Study Day 1) daily. Olanzapine dosing will be selected and titrated by the investigator based upon individual subject needs and consistent with current clinical practice. Subjects will be randomized in a 1:1:1:1 ratio to receive either samidorphan (5, 10, or 20 mg) or placebo.

Part B will include an additional 12-week treatment period where all subjects will receive active olanzapine + samidorphan (ie, ALKS 3831). Subjects randomized to samidorphan during Part A will continue receiving the same dose of samidorphan during Part B. Subjects randomized to placebo during Part A will receive the highest dose of samidorphan during Part B. Dose level during Part B will be double-blind. For all subjects, samidorphan dosing will stop at the end of Part B, but olanzapine dosing will continue uninterrupted through a 4-week follow-up period, which includes 2 safety visits.

This study will use an independent Data Safety Monitoring Board (DSMB) to monitor subject safety data. After at least one week of safety data has been collected for 40 randomized subjects, the DSMB will review the accumulated safety data for all subjects. After at least one week of safety data has been collected for 150 randomized subjects, the DSMB will review the accumulated safety data for all subjects. Additional reviews of the data may occur at the discretion of the DSMB. Complete details of the data review procedures of the DSMB are available in the DSMB charter.

This is the first study of ALKS 3831 in a population of adults with schizophrenia. Subjects will be monitored in an inpatient setting for 2 nights following randomization (Visit 3) and during the transition from Part A to Part B (Visit 13). These are the two periods where samidorphan treatment may be initiated. Subjects will be monitored in an inpatient setting whether or not samidorphan treatment is being initiated in order to maintain double-blind dosing and a consistent subject experience consistent across treatment groups.

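### Taken literally, SAP 3.7.6 starts the Part B concomitant-medication window at Day 8 in the three samidorphan arms but at Day 92 in the former placebo arm

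*SAP*

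**What the plan says.** SAP 3.7.6 sets two windows for concomitant medications. The Part A window covers medications taken "between the first dose of the randomized medication to the end of Part A treatment period (inclusive"). The Part B window covers those taken "between the first dose of the samidorphan to the end of Part B treatment period (inclusive"). The Part B sentence is labelled as applying to the Part B ALKS 3831 treatment period, but the start it gives is tied to neither Part B nor Visit 13.

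The same section fixes the layout and the counting: "Prior and concomitant medications will be summarized by the Preferred Term and by treatment group", and with repeated use "the subject will be counted only once for the medication". Any use within the window is therefore enough to count a subject.

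The date of the first samidorphan dose depends on the arm. Protocol 9.3 states: "On Day 8 (Visit 3), subjects will be randomized to receive one of the following regimens in a 1:1:1:1 ratio". SAP 1.2 adds "Subjects randomized to samidorphan during Part A will continue receiving the same dose of samidorphan during Part B", and for the other arm "Subjects randomized to placebo during Part A will receive the highest dose of samidorphan during Part B". The Protocol Synopsis fixes the boundary: "Transition (Visit 13) is the end of Part A and the beginning of Part B (Part B begins with dosing at Visit 13").

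**The concern.** The first samidorphan dose marks the start of Part B only for subjects who had placebo in Part A. For the other three arms it marks the start of Part A. A programmer who follows the sentence as written would derive a valid date for every subject and see no error, yet the table headed Part B would hold Part A and Part B together in three columns and Part B alone in the fourth.

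The distortion concerns medications that stopped during Part A. Protocol 8.1.1 makes some of these likely. Prior antipsychotics are cross-tapered by Day 15, a week after randomization, so one still being taken after the first randomized dose would appear as a Part B medication in the samidorphan columns and not in the former placebo column. A reader could take that as additional antipsychotic use alongside ALKS 3831 in Part B. Short courses of the hypnotics or benzodiazepines that Protocol 8.4.1 permits would be misplaced in the same way.

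**Working it through.** **Inputs.** The visit days come from the schedules in the Protocol Synopsis and Protocol 8.2:
- Visit 3 (randomization, first samidorphan or placebo dose): Day 8.
- Visit 13 (start of Part B dosing): Day 92.
- Visit 23 (end of Part B): Day 176, with the last samidorphan dose the night before, on Day 175.

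**The plan's own period lengths.** Part A is (92 − 8)/7 = 12.0 weeks and Part B is (176 − 92)/7 = 12.0 weeks. Both agree with the two 12-week periods in the Synopsis.

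**The Part B medication window as written, for subjects who complete Part B.**
- 5, 10 and 20 mg arms: 176 − 8 = 168 days = 24.0 weeks.
- Former placebo arm: 176 − 92 = 84 days = 12.0 weeks.

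Counting dosing days instead gives the same figures: 175 − 8 + 1 = 168 and 175 − 92 + 1 = 84. The visit tolerances (±1 day at Visit 3, ±2 days at Visits 13 and 23) move the lengths to between 23.6 and 24.4 weeks and between 11.4 and 12.6 weeks. The ratio stays close to 2 to 1. Subjects who leave Part B early have shorter windows.

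**Effect on the percentages.** The documents give no rates of medication use, so what follows is an illustration. Let p be the proportion starting a given medication in each 12-week period, independently between periods and equal in all arms. Let f be the fraction of Part A starters still taking it on Day 92. The SAP counts medications taken in the window, whether or not they were started in it, so:
- samidorphan arms, literal window: 1 − (1 − p)²
- former placebo arm: 1 − (1 − p)(1 − pf)
- gap: p(1 − p)(1 − f)

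With p = 0.15, the samidorphan arms show 1 − 0.85² = 27.8% whatever the value of f. The former placebo arm shows:

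| Part A starters still on the medication at Day 92 | Former placebo arm | Gap |
|---|---|---|
| None (f = 0) | 15.0% | 12.8 points |
| Half (f = 0.5) | 1 − 0.85 × 0.925 = 21.4% | 6.4 points |
| All (f = 1) | 27.8% | 0 |

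At the extreme f = 0, other values of p give 9.75% versus 5%, 19% versus 10%, 36% versus 20%, and 51% versus 30%. At f = 1 the gap is zero for every p.

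**With the window started at Visit 13.** It is (176 − 92)/7 = 12.0 weeks in all four arms, and under the same assumptions the expected percentages are equal.

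**The case against.** The strongest reply is that the intent is clear from context. The sentence defines medications for the Part B period, and a Day 8 start would contradict that label. SAP 3.1.1 ties the Part B baseline to the Visit 13 dose, SAP 3.2.3 requires a dose in Part B for the Part B safety population, and SAP 3.7.2.1 keeps Part A, Part B and combined periods apart for adverse events. The mock tables are in a separate document (SAP 4), so what will be programmed cannot be known from these documents. All of this stands as evidence of intent. It does not change the operative definition, which names a different start and can be applied without any query arising.

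A reader might infer more: that the Part B table will certainly span 24 weeks in three arms, and that it will show a false excess of about 13 percentage points. The documents do not support either. The first treats one reading as settled. The second treats the extreme case as the expected one. Because medications are counted when taken, only those stopped before Day 92 create an imbalance. Protocol 8.4.1 asks that benzodiazepine doses for agitation or anxiety be kept as stable as possible through the study, and such continuing use counts in every arm under either reading. Under SAP 3.11.5 a medication with a completely missing stop date is treated as ongoing, so it too counts in every arm.

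Nor is appearing in both period tables an error in itself. A medication that continues across Day 92 belongs in both, also after the fix.

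The consequence is limited as well. No test, endpoint or analysis set uses this table, start and stop dates are collected (Protocol 8.3.5), and all reported medications are listed.

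**Conclusion.** The point holds as a defect in the wording of a definition, at low severity. Read literally, the Part B window is 168 days in the 5, 10 and 20 mg arms and 84 days in the former placebo arm, for subjects who complete Part B. Medications stopped before Day 92 would then count as Part B use in three arms only. The label and the rest of the SAP suggest that the first Part B dose was meant, but SAP 3.7.6 does not say so.

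The day counts rest on the documents alone. The percentages rest on an assumed 15% starting rate per 12 weeks, equal across arms and independent between periods. They run from a gap of 12.8 points down to none, depending on how many Part A medications continue past Day 92. The illustration leaves out medications already in use at Day 8; those stopped before Day 92, such as tapered antipsychotics, would be misplaced in the same direction. SAP 3.7.6 does not name the population for this table. The comparison here assumes subjects who entered Part B.

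**What to change.** In SAP 3.7.6, define the Part B window for all arms as running from the first dose of study drug in Part B, at Visit 13 (Day 92), through the last day of the Part B treatment period. This matches the anchor in SAP 3.1.1 and gives 12 weeks in every arm. If a summary over both parts is wanted, present it as a separate table labelled as combined, as SAP 3.7.2.1 does for adverse events. The cost is one phrase in the SAP and a check that the table specification uses the same start date. No additional data are needed.
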